### **6.7.5. Subjects Entering the Study on Prophylactic HAE Medications**

Any subject who took Berinert, Ruconest, Haegarda, or Cinryze (all C1-inhibitors or C1-esterase inhibitors [C1-INH]) on Study Day 1 with regular frequency of administration (eg, once weekly, twice weekly, etc.) or tranexamic acid taken daily and *not* flagged on the concomitant medications eCRF as ‘PRN’ are considered to be on current prophylactic medication.

### **6.7.6. Visit Windows**

For summary purposes in general, records will be assigned to the scheduled visit collected on the eCRF. Unscheduled and early termination visits will be assigned to an analysis window

according to the study day of the actual visit date using the visit windows displayed in [Table 5](#). All information collected at an unscheduled visit will be identified as such in the listings.

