8.3.2. Subject Discontinuation from Study Drug

A subject will be permanently withdrawn from study drug for any of the following bulleted reasons, which will be recorded in the source documents and CRF. When medically feasible, the Medical Monitor must be consulted prior to subject discontinuation. In all cases, subjects who prematurely and permanently discontinue study drug should complete all scheduled procedures for the end-of-study visit outlined in Table 3.

- Emergence of any laboratory abnormality or AE that in the judgment of the Investigator compromises the ability of the subject to continue study-specific procedures or it is considered not to be in the subject's best interest due to an altered benefit-risk profile
- Reoccurrence of treatment-emergent AST or ALT elevation $> 5 \times \text{ULN}$ (confirmed) if BCX7353 is restarted after meeting hold criteria as outlined in Section 12.2.2.
- Treatment-emergent ALT or AST $> 3 \times \text{ULN}$ combined with either laboratory abnormalities indicative of significant hepatic toxicity (ie, meeting Hy's law, total bilirubin $> 2 \times \text{ULN}$ OR with an INR > 1.5) or with symptomatology of acute hepatitis (ie, severe fatigue, nausea, vomiting, right upper quadrant pain and tenderness, fever, rash, and/or eosinophilia [$> 5\%$])
- Subsequent determination that inclusion/exclusion criteria were not met
- Intercurrent illness or emergence of a new illness/medical condition that would, in the judgment of the Investigator, affect assessments of clinical status to a significant degree
- Subject noncompliance with study drug or to the protocol
- Subjects with BCX7353-related Grade 3 or 4 rash as described by the Division of Microbiology and Infectious Diseases (DMID) criteria "skin-mucocutaneous" will be discontinued from study, if suspected to be due to BCX7353, and treated according to best medical practice. All subjects with a suspected drug rash should undergo specific rash evaluation as described in Section 11.1.12. A Grade 3 rash is defined as vesiculation or moist desquamation or ulceration, and a Grade 4 rash is defined as exfoliative dermatitis, mucous membrane involvement or erythema multiforme or

suspected SJS or necrosis requiring surgery. Subjects with a Grade 1 or 2 study drug-related rash may continue BCX7353 if the Investigator and subject deem it appropriate.

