10.3.5. End of Study Visit

Subjects who discontinue study drug will return to the clinic 3 weeks (21 ± 3 days) after the date of their last dose for their end of study or withdrawal assessment. Subjects who discontinue study drug must undergo all study-related procedures outlined in [Table 3](#). Subjects who discontinue the study but will continue to receive BCX7353 via another mechanism will have end-of-study assessments performed at their last regularly scheduled visit.

If an AE is ongoing at the end of study visit, additional clinic visit(s) or telephone contact(s) may be warranted (see Section [12.1.2](#)).

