**Table 3: Schedule of Clinical Assessments**

Assessment	Screening Period	Baseline Visit a	Treatment Period (Visit schedule)					End of Study Assessment
	Screening Visit (Up to Day -28)	(Day 1)	Week 2 (Day 15 ± 2 days) b	Week 4 (Day 29 ± 2 days)	Week 8 (Day 57 ± 2 days)	Week 12 (Day 85 ± 2 days)	Visits every 12 weeks until 96 weeks (± 6 days)	3 weeks (± 3 days) after last dose of study drug
Informed consent c	X	X						
Clinic staff phone call/ communication							X d	
Inclusion-exclusion criteria	X	X						
Medical and medication history, HAE medical and medication history e	X	X						
Weight/height/BMI f	X	X		X	X	X	X	X
Drugs of abuse screen g	X							
Physical examination h	X	X		X	X	X	X	X
Pregnancy test i	X	X		X	X	X	X	X
Vital signs j	X	X		X	X	X	X	X
FSH k	X	X						
HIV, HCV, HBV serology	X							
Diagnosis of HAE established l	X							
Clinical chemistry/hematology/coagulation g	X	X	X b	X	X	X	X	X
Troponin I and Troponin T, CK-MB		X		X	X	X	X	X
NGAL and ACR		X				X	X	X
Urinalysis g	X	X	X b	X	X	X	X	X

b The Week 2 visit will consist of monitoring liver function tests only [ALT, AST, GGT, total and direct bilirubin, ALP]; urine and additional tubes of blood may be required to accommodate reflex testing for abnormal GGT (see protocol Table 7). If preferred by the subject and clinical site, laboratory values may be drawn and resulted locally, with results entered into the CRF.

c Informed consent will be signed at the screening visit for subjects requiring a screening visit and will be signed for all other subjects at the baseline visit or final on treatment visit in the parent study (which serves as the subject's baseline visit in this study).

d After the Week 12 visit, clinic staff must contact the subjects at least once every 4 weeks between clinic visits to assess the subject's overall wellbeing and any issues with regards to study drug tolerability. During all calls, sites will also discuss study drug compliance and any issues with the diary or study drug.

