### 6.7.7. Multiple Assessments

Where multiple scheduled measurements are recorded for a given time point (ie, triplicate ECGs or repeated blood pressure assessments), the mean of the measurements will be calculated and used in any derivation of summary statistics. All available data will be listed.

When multiple visits occur within the same window, the scheduled visit will be used in the analysis if available. If no scheduled visit occurs within the window and unscheduled visit(s) and/or an early termination visit occur within the window, the analysis visit closest to the target day will be selected for use in analysis. If deemed appropriate by the sponsor (eg, in the case of a

retest), unscheduled visits may be chosen for analysis given documentation of the desired visit from the sponsor.

Results from unscheduled visits will be eligible for inclusion in analyses of worst post-baseline results regardless of their use for ‘by visit’ displays.

Listings will display all visits as recorded on the eCRF, including the date and study day. All available data including any totals, domains, or subscales of scale assessments summarized will be listed.

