## **9.6. Laboratory Data**

The following is a safety endpoint:

- Number and proportion of subjects who experience a treatment-emergent Grade 3 or 4 laboratory abnormality

A listing of clinical laboratory evaluations is provided in protocol Section 11.1.6.

Clinical laboratory assessments and corresponding changes from baseline will be summarized for each laboratory panel by treatment group and visit. Laboratory abnormalities will be graded according to the DMID Adult Toxicity Table (publish date: November 2007; see Protocol Appendix 16.1). Any graded abnormality that occurs following the initiation of study drug and represents at least one-grade increase from the baseline assessment is defined as treatment emergent.

Urinalysis results will be summarized by treatment and visit and listed by subject and treatment.

The number and percentage of subjects experiencing treatment-emergent graded toxicities will be summarized. Treatment-emergent Grade 3 or 4 laboratory abnormalities will be summarized separately. Laboratory toxicity shifts from baseline to worst post-baseline assessments will be summarized.

The number and percentage of subjects having elevations in liver enzyme abnormalities (alanine aminotransferase [ALT], aspartate aminotransferase [AST], or bilirubin) in relation to fold above the upper limit of normal (ULN) will be summarized by treatment group.

The following categories of abnormal hepatic laboratory values will be evaluated for any occurrence among all post baseline assessments (where “and” indicates elevations occurring at the same visit). Within each treatment group and laboratory parameter grouping, a subject may be counted once per elevation criteria using the worst-case result. That is, a subject with a worst-case ALT elevation  $>3 \times$  the ULN for a given treatment group would be counted once in the ALT  $> 1.5 \times$  ULN category and once in the ALT  $> 3 \times$  ULN category, regardless of how many ALT elevations the subject had that met the  $> 3 \times$  ULN and  $> 1.5 \times$  ULN elevation criteria.

- ALT and/or AST > 3 × ULN and total bilirubin > 1.5 or 2 × ULN
- AST > 1.5, 3, 5, 10, and 20 × ULN
- ALT > 1.5, 3, 5, 10, and 20 × ULN
- Total bilirubin > 1, 1.5, or 2 × ULN
- Alkaline phosphatase (ALP) > 1.5 × ULN

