### **9.8. Vital Signs**

Vital signs (systolic and diastolic blood pressure, pulse rate, temperature, and respiratory rate) and body weight and corresponding changes from baseline will be summarized by treatment group and visit using descriptive statistics. These data will be listed by subject, treatment, and visit.

Distribution plots of systolic and diastolic blood pressure over time will be produced using the format recommended by the FDA/Industry/Academia Safety Graphics working group (<https://www.ctspedia.org/do/view/CTSpedia/StatGraphHome>). The graph format to be used is the same as the graph provided for the distribution of ALT by time and treatment.

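### Early termination visits are windowed by study day with no reference to last dose, so by-visit laboratory and vital-sign means can include off-drug values (minor)

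*SAP*

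**What the plan says.** **Windowing rule.** SAP 6.7.6 keeps records in general under the scheduled visit entered on the eCRF, then adds: "Unscheduled and early termination visits will be assigned to an analysis window", using the study day of the visit date and the Table 5 windows. Study day counts from first dose (SAP 6.7.2). Table 5 runs from screening to Week 96, whose window is open-ended from Day 632. It has no end-of-study or follow-up row.

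**Selection rule.** SAP 6.7.7 prefers a scheduled visit. "If no scheduled visit occurs within the window and unscheduled visit(s) and/or an early termination visit occur within the window", it takes the visit closest to the target day. Last dose is not a condition. The sponsor's discretion to choose a different record covers unscheduled visits only.

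**The visit after stopping drug.** Protocol 8.3.2 says "subjects who prematurely and permanently discontinue study drug should complete all scheduled procedures for the end-of-study visit outlined in Table 3". Protocol 10.3.5 brings these subjects back 21 ± 3 days "after the date of their last dose for their end of study or withdrawal assessment". The End of Study column of SAP Table 3 is timed "3 weeks (± 3 days) after last dose of study drug" and is marked for "Clinical chemistry/hematology/coagulation", urinalysis and vital signs.

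**Where the values go.** SAP 9.6: "Clinical laboratory assessments and corresponding changes from baseline will be summarized for each laboratory panel by treatment group and visit". SAP 9.8 says vital signs "and body weight and corresponding changes from baseline will be summarized by treatment group and visit using descriptive statistics". Neither sets an on-treatment limit.

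**The concern.** The SAP does not say which visit the early termination visit is. The only visit that either document describes after study drug is stopped is the end-of-study or withdrawal assessment about three weeks later. If that is the visit meant, the windowing rule places an off-drug value in whichever treatment week its study day falls in. For example, a last dose on Day 120 gives an assessment on about Day 141. This lies in the Week 24 window (Days 128 to 211), no Week 24 visit has taken place, and the value enters the Week 24 mean.

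Other parts of the SAP do use the end of dosing as a limit. Attack rates stop one day after last treatment (6.7.8.3), the Kaplan-Meier safety analyses censor at last dose (9.3.2, 9.3.3, 9.6), and treatment-emergent events stop 30 days after discontinuation (9.3). The visit windows have no such limit.

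Long-term safety is the primary objective, and by-visit tables are one way of describing it over time. At stake is whether a mean labelled as a treatment week describes people on treatment.

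**Working it through.** The plan gives no figure for this point. The protocol's discontinuation percentages do reproduce: 59/227 = 26.0% overall, 57/227 = 25.1% before 48 weeks, and 28/227 = 12.3% for perceived lack of efficacy (Protocol 5.2.2).

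**Step 1: when is the off-drug record selected?** For a last dose on day L, put the assessment on day L + 21 and find its Table 5 window. It is selected if that window's scheduled visit had not occurred by day L. Scheduled visits are taken on their target days under the SAP schedule.

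- L = 1: Week 2 window. L = 2–22: Week 4. L = 23–50: Week 8. L = 51–84: Week 12. In each case the scheduled visit is still to come, so 1 + 21 + 28 + 34 = 84 of 84 days. If the Week 12 visit is held on Day 83, it is 82 of 84.
- L = 85–106: the Week 12 window already holds its Day 85 visit, so the record is not selected (22 days). L = 107–168: Week 24 window before the Day 169 visit, so it is selected (62 days). The pattern repeats every 84 days: 3 × 62 = 186 of 252 for Days 85–336, or 73.8%.
- Varying the lag from 18 to 24 days and the visits from the early to the late edge of tolerance gives 159/252 = 63.1% to 209/252 = 82.9%.
- Days 1–672: 84 + 7 × 62 = 518 of 672, or 77%. On the current protocol's sparser schedule it is 584/672 = 87%.

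**Step 2: stops on a visit day.** With a 21-day lag, a stop at Week 2 (Day 15) gives Day 36, at Week 4 gives Day 50, and at Week 8 gives Day 78. Each lands in the next window and is selected. A stop at Week 12 gives Day 106 and at Week 24 gives Day 190. These, like all later visit-day stops, stay in their own window and are not selected. Clustering of later stops on visit days would therefore lower the 74%, to zero at the extreme.

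**Step 3: illustrative Week 12 laboratory counts.** Of 57 stops before Week 48, 28 were for lack of efficacy, 20 of those before Week 12 (Protocol 5.2.2). The shortest exposure was 11 days, so early last doses span Days 11–84 (74 days), of which 34 land in the Week 12 window. Everyone not stopped early is assumed to have a Week 12 value.

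| Stops before Week 12 | Basis | Off-drug records | Share of Week 12 values |
|---|---|---|---|
| 20 | only the documented early lack-of-efficacy stops | 20 × 34/74 = 9.2 | 9.2/(207 + 9.2) = 4% |
| 41 | all 57 split as 20/28 (40.7) | 40.7 × 34/74 = 18.7 | 18.7/(186.3 + 18.7) = 9% |
| 49 | 57 less the 8 later lack-of-efficacy stops | 49 × 34/74 = 22.5 | 22.5/(178 + 22.5) = 11% |

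These assume an even spread of last doses and full attendance. They are scenarios, not bounds.

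**Step 4: questionnaires, where collected.** The pooled Week 48 AE-QoL improvement is (30 × 12.8 + 73 × 14.7)/103 = 14.1 points. If all 57 stops are spread over Days 1–336, 57 × 62/336 = 10.5 records fall in the Week 48 window, a share of 10.5/(103 + 10.5) = 9.3%. Assuming full return to baseline, the mean shifts by 0.093 × 14.1 = 1.3 points, against the 6-point MCID in Protocol 5.2.2. If later stops fall on visit days it is 0.

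**The case against.** **The premise may be wrong.** SAP Table 3 gives the End of Study assessment its own column, timed from last dose, and that column is not limited to early withdrawals. If the eCRF records it as a scheduled visit, the opening sentence of 6.7.6 keeps that label and nothing is misplaced. Its absence from a study-day table would then be unremarkable. This stands as a real alternative, and the eCRF would settle it. It does not remove the need for a change, because early termination visit would then refer to no visit that the documents describe, and Table 5 would still have no row for the assessment.

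**It matters little.** The summaries are descriptive, no formal testing is planned (SAP 8.1), and off-drug values can be traced because listings carry visit dates, study days and last-dose dates. This also stands, and it limits the point to a minor one. No shift in any laboratory or vital-sign mean can be derived from the documents.

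**The questionnaire effect mixes versions.** The SAP's revision table ends at Protocol Version 5.0, and SAP Table 3 footnote o does not list the end-of-study visit for AE-QoL and TSQM. The current protocol does (Table 3 footnote o and 11.2.1). The effect is therefore conditional, as well as small.

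**Attendance is uncertain.** Protocol 8.3.1 only requests the visit, whereas 10.3.5 requires the procedures. If nobody attends, the effect is zero.

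**A general cut-off would go too far.** It is tempting to move every assessment made more than one day after last dose out of the treatment weeks. The documents do not support that. The one-day allowance belongs to the attack-rate calculation, treatment-emergent events run to 30 days, and such a cut-off would override scheduled-visit labels that 6.7.6 keeps.

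**Conclusion.** The point holds as a minor one. As written, and on the natural reading of an undefined term, SAP 6.7.6 and 6.7.7 can report laboratory and vital-sign values taken about three weeks after last dose as treatment-week values. With evenly spread last doses and full attendance, this applies to all or nearly all stops before Day 85 and to about 74% (63 to 83%) of stops on Days 85 to 336. In the illustrative scenarios, about 9, 19 or 23 such records make up 4, 9 or 11% of the Week 12 laboratory values.

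A reader might infer that the safety conclusions are biased. The documents do not support this. Endpoint proportions, worst-post-baseline tables, Grade 3/4 results and Kaplan-Meier estimates do not depend on the visit label, and the direction of any shift in the by-visit means is not established. Nor can a reader conclude that mislabelling is certain, since that depends on how the eCRF records the visit.

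**What to change.** In SAP 6.7.6, state that the end-of-study or withdrawal assessment made after permanent discontinuation of study drug is summarized in its own Table 5 row, *End of study / post-treatment*. State also that it is not assigned to a treatment-week window under 6.7.6 or 6.7.7.

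- Leave under their eCRF labels all other scheduled visits, and the end-of-study assessments of subjects who continue BCX7353 by another route (made at their last regular visit, Protocol 10.3.5).
- Add no general last-dose cut-off for other assessments.
- Keep every value in the listings and worst-post-baseline tables, so that the commitment in SAP 6.8.1 to use all available data is still met.
- Show the number discontinued beside each treatment-week mean.

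The cost is SAP wording and programming. No visit or data collection changes, and no data are lost. The downside is that treatment-week means then largely describe subjects still on drug, which is why the discontinuation counts should sit beside them.

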**Table 5: Visit Windows (Days)**

Visit	Relative Target Day	Protocol-Specified Visit Window	Analysis Visit Window
Screening visit		-28 to -1	-28 to -1
Baseline visit	1	1	1
Week 2 (Day 15)	15	12 – 18	2 – 22
Week 4 (Day 29)	29	27 – 31	23 – 43
Week 8 (Day 57)	57	55 – 59	44 – 71
Week 12 (Day 85)	85	83 – 87	72 – 127
Week 24 (Day 169)	169	163 – 175	128 – 211
Week 36 (Day 253)	253	247 – 259	212 – 295
Week 48 (Day 337)	337	331 – 343	296 – 379
Week 60 (Day 421)	421	415 – 427	380 – 463
Week 72 (Day 505)	505	499 – 511	464 – 547
Week 84 (Day 589)	589	583 – 595	548 – 631
Week 96 (Day 673)	673	667 – 679	≥ 632

In certain presentation, the HAE attack rates are analyzed by month. The HAE attack will be assigned to an analysis month according to the study day of the actual HAE attack using the following conventions:

Attack Day	Analysis Month for Display
1 – 28	Month 1 (Day 1 – 28)
29 – 56	Month 2 (Day 29 – 56)
57 – 84 a	Month 3 (Day 57 – 84)

a Continues for additional months (28-day blocks) through the end of the study.

### 6.7.7. Multiple Assessments

Where multiple scheduled measurements are recorded for a given time point (ie, triplicate ECGs or repeated blood pressure assessments), the mean of the measurements will be calculated and used in any derivation of summary statistics. All available data will be listed.

When multiple visits occur within the same window, the scheduled visit will be used in the analysis if available. If no scheduled visit occurs within the window and unscheduled visit(s) and/or an early termination visit occur within the window, the analysis visit closest to the target day will be selected for use in analysis. If deemed appropriate by the sponsor (eg, in the case of a

retest), unscheduled visits may be chosen for analysis given documentation of the desired visit from the sponsor.

Results from unscheduled visits will be eligible for inclusion in analyses of worst post-baseline results regardless of their use for ‘by visit’ displays.

Listings will display all visits as recorded on the eCRF, including the date and study day. All available data including any totals, domains, or subscales of scale assessments summarized will be listed.

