11.1.3. Weight/Body Mass Index

For determination of height and weight, subjects should be clothed with shoes removed.

BMI should be calculated using the following formula:

$$\text{BMI} = \text{weight (kg)} / \text{height (m)}^2$$

BMI and height are only to be captured at the screening visit. Adolescents will also have height captured at Week 48.

11.1.4. 12-lead Electrocardiograms

A standard bedside or routine 12-lead ECG machine that calculates heart rate and measures the PR, QRS, QT, RR, and QTc (QTcF) intervals will be utilized. Prior to obtaining an ECG, subjects should rest quietly.

Qualified site personnel must review the ECGs and automated findings for gross abnormalities and to review any interval measurements of concern (absolute readings and for post-baseline ECGs, a change from baseline). For all ECGs, the clinical interpretation of the ECG and calculated QTcF (if not automated by the ECG machine and including adjudication of any automated measurements or diagnoses) should be recorded directly on a hard copy of the ECGs. Copies of the ECGs may be requested by the Sponsor. All subject identifiers will be masked prior to provision to the Sponsor.

Baseline (predose) ECGs will be obtained in triplicate (i.e., 3 separate readings taken at 1- to 5-minute intervals), with baseline values calculated from an average of the 3 readings. All other ECGs will be single assessments. ECG readings should be obtained prior to blood sampling.

An ECG should be repeated for a change from baseline in QTcF > 60 msec or a QTcF interval > 500 msec.

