12.2.2. Aminotransferase (ALT or AST) Elevation

All baseline or treatment-emergent ALT or AST elevations $> 3 \times \text{ULN}$ (ie, Grade 3 and above) should be confirmed within 72 hours with repeat assessment of ALT and AST as well as total bilirubin, ALP, prothrombin time /INR, and complete blood count for eosinophil levels. If subjects are asymptomatic with no other pertinent laboratory abnormality, study drug may be continued under close observation with every 2 week assessment of transaminase levels, total bilirubin, and ALP. These may be done at a local laboratory as long as results are reported to the Investigator as soon as they are available and the investigative site contacts the subject to ascertain any symptoms. If either ALT or AST continue to increase and the subject remains asymptomatic, study drug dosing must be held if:

- Either ALT or AST is $> 5 \times \text{ULN}$ for more than 2 weeks
- The ALT or AST reaches $> 8 \times \text{ULN}$

The subject should continue regular assessments as deemed appropriate by the Investigator of ALT, AST, total bilirubin, ALP, prothrombin time/INR, and complete blood count for eosinophil levels until ALT and/or AST are $< 3 \times \text{ULN}$.

Provided specific criteria are met, the Investigator and subject may elect to resume BCX7353 dosing. All of the following criteria must be met for dosing to resume:

- The subject is considered to have been deriving benefit from BCX7353 prior to holding study drug.
- Transaminases return to $\leq 2 \times \text{ULN}$ for subjects whose baseline transaminase levels were above the ULN, and $\leq \text{ULN}$ for those whose baseline transaminase levels were $\leq \text{ULN}$.
- Subjects have not initiated or restarted androgens during the period BCX7353 was held.
- The subject agrees to continue every 2 week monitoring of ALT, AST, total bilirubin, ALP, CBC (eosinophil levels) and prothrombin/INR until levels appear stable and

transaminase levels remain $< 3 \times \text{ULN}$ for at least 1 month after restarting BCX7353 dosing.

If at any time, the criteria as outlined in Section 8.3.2 is met, the study drug must be permanently discontinued.

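### SAP 6.7.7 lets the sponsor put a retest in place of the scheduled result in by-visit safety displays, with no criterion except documentation

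*SAP*

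**What the plan says.** SAP 6.7.7 sets a clear default: "When multiple visits occur within the same window, the scheduled visit will be used in the analysis if available". If the window holds no scheduled visit, the unscheduled or early termination visit nearest the target day is used. The same paragraph then allows an exception at the sponsor's judgement, with a retest as the example: "unscheduled visits may be chosen for analysis given documentation of the desired visit from the sponsor". It gives no criterion, no deadline of its own and no requirement that the choice be made without knowledge of the result. The only timing limit is the general statement in SAP Section 2 that final-analysis decisions precede database lock.

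The section also contains safeguards. "Results from unscheduled visits will be eligible for inclusion in analyses of worst post-baseline results", whether or not they appear in by-visit displays. "Listings will display all visits as recorded on the eCRF, including the date and study day".

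The protocol says when repeats are taken:

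- Section 12.2: clinically significant Grade 3 and 4 laboratory abnormalities are to be confirmed by repeat testing.
- Section 12.2.2: ALT or AST above 3 x ULN "should be confirmed within 72 hours with repeat assessment of ALT and AST".
- Section 11.1.4: "An ECG should be repeated for a change from baseline in QTcF > 60 msec or a QTcF interval > 500 msec".

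**The concern.** The repeats that the protocol prescribes follow abnormal results. The exception will therefore be available mostly where the scheduled value was high, and whoever uses it can see both values. A measurement repeated because it was extreme tends to be less extreme the second time, through measurement error and within-subject variation alone, so discretionary replacement has a predictable direction. Documenting each choice makes it traceable but does not make it independent of the result.

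At stake are the displays that show time trends in a long-term safety study: laboratory values and changes by visit, the liver-test distribution plots (SAP 9.6), vital signs and blood-pressure plots (SAP 9.8), and ECG changes by visit with the QTcF plot (SAP 9.9). The chemistry summaries are repeated by time since stopping androgens and by duration of androgen use (SAP 13.1, Tables 14.3.5.1.2 and 14.3.5.1.3). That is where the protocol locates its main liver question (Sections 5.4.3 and 5.7).

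**Working it through.** The study has no sample-size, alpha or power figure that bears on this, so the check is a reading of the text followed by a short illustration.

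**1. Does a retest compete with the scheduled result?** Yes. An ALT repeat is due within 72 hours. A Week 12 visit on Day 85 with a repeat by Day 88 falls inside the Week 12 analysis window of Days 72 to 127 (SAP Table 5). The default keeps the Day 85 value; the exception allows the later one.

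**2. Which analyses depend on the record chosen?**

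- *Dependent:* by-visit summaries and changes from baseline for laboratory tests, vital signs and ECG. The distribution plots over time are also dependent, assuming they use the by-visit records, which the SAP does not state. For vital signs the protocol sets no abnormality-driven repeat, so the exception applies but the selection argument is weaker.
- *Not dependent:* the treatment-emergent Grade 3/4 laboratory endpoint, which rests on "Any graded abnormality that occurs following the initiation of study drug" with at least a one-grade rise from baseline; the liver fold-ULN categories, which "will be evaluated for any occurrence among all post baseline assessments"; the plot of maximum transaminase against maximum bilirubin; the Kaplan-Meier analyses of Grade 3 or higher ALT, AST and bilirubin; and the listings.
- *QTcF category table:* SAP 9.9 adds unscheduled ECGs. It does not say that a displaced scheduled ECG stays in, but nothing removes it.

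**3. Size of the effect on a visit mean.** Inputs from Protocol 5.2.2: 227 treated subjects, of whom 13 had treatment-emergent Grade 3 or 4 ALT. Check: 13/227 = 5.7%, as stated there. If k scheduled values are each replaced by a retest lower by d x ULN, and all N subjects contribute to the visit, the mean falls by k x d / N. The documents give no retest values, so d is assumed.

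| k | N | d (x ULN) | Fall in mean (x ULN) |
|---|---|---|---|
| 1 | 227 | 1 | 1/227 = 0.004 |
| 13 | 227 | 1 | 13/227 = 0.06 |
| 13 | 227 | 2.5 | 32.5/227 = 0.14 |
| 13 | 227 | 4 | 52/227 = 0.23 |

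The last three rows are upper illustrations: all 13 subjects peak at the same visit, all 13 are overridden, and every retest is lower. In every row the Grade 3/4 ALT count stays at 13.

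**4. Androgen subgroup.** Protocol 5.2.2 reports 40 subjects who stopped androgens in the 2 weeks before starting study drug. It says all but one of the 13 stopped 7 to 9 days from first dose, read here as before it, which puts 12 in this group. On the same assumptions the subgroup's visit mean would fall by 12 x 1/40 = 0.30, 12 x 2.5/40 = 0.75 or 12 x 4/40 = 1.20 x ULN. The smaller denominator makes the subgroup display more sensitive than the pooled one.

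**The case against.** The strongest reply is that little of importance is exposed. The six safety endpoints in SAP 3.2.1 are proportions of subjects; none is a by-visit mean or a plot. No formal testing is planned. Each override must be documented, all visits are listed, and unscheduled records are identified as such in the listings (SAP 6.7.6), so a substitution can be traced. This stands, and it sets the severity.

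The illustration can also be called a stacked worst case. That stands too: the protocol gives neither the timing of the 13 elevations nor any retest value, and Section 12.2.2 provides for transaminases that keep rising, so a repeat may be higher. For ECGs, the interim summary describes unremarkable findings, so QTcF-triggered repeats may be few.

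Finally, the default works at visit level. If the scheduled visit took place but one analyte was not obtained, the discretion lets a redraw fill the gap. Simply deleting the sentence would lose that, so the replacement rule has to work parameter by parameter.

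None of this supplies a criterion for choosing a retest over a valid scheduled value. Traceability and a decision before lock do not make the choice blind to the result when results are visible throughout and interim analyses are planned (SAP 5.1).

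**Conclusion.** The point holds for by-visit displays and is minor. SAP 6.7.7 permits result-dependent replacement of a valid scheduled value. The protocol's repeat rules mean it would fall mainly on abnormal laboratory and ECG values, with an average pull towards less extreme ones. The pooled effect on a visit's mean ALT ranges from negligible for a single replacement to 0.06 to 0.23 x ULN under the assumed upper illustration; it is larger in the recent-androgen subgroup on the same assumptions. Nothing in the documents suggests that the exception has been misused.

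Two stronger readings are not supported:

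- *That abnormal values could disappear from the safety endpoints.* If replaced values were dropped everywhere, five replacements could take Grade 3/4 ALT from 13 to 8 of 227 (3.5%). The SAP contains no such removal: grading and fold-ULN categories do not depend on the by-visit record. A small gap in wording remains, because the worst-value sentence in 6.7.7 names only unscheduled results and does not say that a displaced scheduled result stays eligible.
- *That the upper tail of the distribution plots would vanish.* It could shrink. A fall of 1 x ULN still leaves any value of 4 x ULN or more at Grade 3 or above (Grade 3 starts at 3.0 x ULN, Protocol Appendix 16.1), and some retests may be higher.

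**What to change.** Replace the exception in SAP 6.7.7 with a fixed rule:

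- By-visit displays use the scheduled result whenever one exists for that parameter.
- An unscheduled result is used only if the scheduled result is missing for that parameter, or if the sample or tracing was reported unusable without reference to its value.
- Each such use is logged.
- Displaced scheduled results stay in all worst-value and categorical analyses, including the QTcF categories.

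The nearest-to-target fallback for windows without a scheduled visit can stay. The cost is a few SAP sentences and the loss of case-by-case flexibility. No new data collection is needed.
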